3.4. Duration of Treatment

Participants will be treated with RDV or saline as placebo for up to 5 days.

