5.3. Dosage and Administration of Remdesivir

Remdesivir for injection, 100 mg, will be provided by Gilead.

Participants in Treatment Group A will receive IV RDV 200 mg on Day 1 followed by IV RDV 100 mg once daily on Day 2 up to Day 5. Participants in Treatment Group B will receive IV saline as placebo on Day 1 followed by IV saline as placebo once daily on Day 2 up to Day 5.

Remdesivir will be administered via IV infusion over 30 to 120 minutes. Refer to the pharmacy manual for details. For participants on intermittent hemodialysis, if dosing falls on the same day as the hemodialysis session, RDV will be administered before initiation of the hemodialysis.

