7.7. Toxicity Management

Infusion-related reactions have been observed during and following administration of RDV. Signs and symptoms may include hypotension, hypertension, tachycardia, bradycardia, hypoxia, fever, dyspnea, wheezing, angioedema, rash, nausea, diaphoresis, and shivering. Slower infusion rates, with a maximum infusion time of up to 120 minutes, can be considered to potentially prevent these signs and symptoms. If signs and symptoms of a severe infusion-related reaction occur, immediately discontinue administration of RDV and initiate appropriate treatment. Remdesivir infusions will be administered to participants at the site under close supervision. Healthcare professionals administering RDV infusions must have the appropriate medication available for immediate use in case of hypersensitivity or infusion-related reactions. The participant should be treated according to the SOC for management of hypersensitivity reaction or infusion-related reactions. Participants should be monitored for at least 2 hours after the RDV infusion is completed.

All clinical events and clinically significant laboratory toxicities will be managed according to uniform guidelines detailed in [Appendix 6](#), and as outlined below.

Grade 3 or 4 clinically significant laboratory abnormalities that were not present at baseline should be confirmed by repeat testing as soon as possible, and preferably within 3 calendar days after receipt of the original test results.

The Gilead medical monitor should be consulted prior to investigational drug discontinuation when medically feasible.

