7.1.5. Treatment-Emergent Adverse Events

7.1.5.1. Definition of Treatment-Emergent Adverse Events

Treatment-emergent adverse events (TEAEs) are defined as 1 or both of the following:

- Any AEs with an onset date on or after the study drug start date and no later than 30 days after permanent discontinuation of study drug
- Any AEs leading to premature discontinuation of study drug.

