7.1.6. Summaries of Adverse Events and Deaths

TEAEs will be summarized based on the Safety Analysis Set.

A brief, high-level summary of the number and percentage of participants who experienced at least 1 TEAE in the categories described below will be provided by treatment group. Treatment-emergent deaths observed in the study will also be included in this summary.

Treatment-emergent death refers to deaths that occurred between the first dose date and the last dose date plus 30 days (inclusive).

The number and percentage of participants who experienced at least 1 TEAE will be provided and summarized by SOC, High level term (HLT), PT, and treatment group.

For other AEs described below, summaries will be provided by SOC, PT, and treatment group:

- TEAEs with Grade 3 or higher
- TE study drug-related AEs
- TE study drug-related AEs with Grade 3 or higher
- TE SAEs
- TE study drug-related SAEs
- AEs leading to premature discontinuation of study drug

Multiple events will be counted only once per participant in each summary. Adverse events will be summarized and listed first in alphabetic order of SOC (and HLT within each SOC if applicable), and then by PT in descending order of total frequency within each SOC. For summaries by severity grade, the most severe grade will be used for those AEs that occurred more than once in an individual participant during the study.

In addition to the above summary tables, all TEAEs, TEAEs with Grade 3 or higher, TE study drug-related AEs, TE study drug-related AEs with Grade 3 or higher, and TE SAEs will be summarized by PT only, in descending order of total frequency.

The above summary tables may also be provided for one or more of the following subgroups: kidney disease status (as defined in Section 3.4), high-flow oxygen requirement (Yes, No), and/or region (US, ex-US).

In addition, data listings will be provided for the following:

- All AEs
- All study drug-related AEs
- All AEs with severity of Grade 3 or higher
- All SAEs
- All study drug-related SAEs
- All Deaths
- AEs leading to premature discontinuation of study drug

Listing of renal and hepatic adverse events will be provided. Hypersensitivity including infusion-related reactions adverse events will also be summarized and listed (See [Appendix 2](#)).

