01612908001	12759201001	14407901001	01601501001	
14022001001	14032001001	14997401001	14972001001	
14156901001	14032401001	14151801001	13978201001	
14149701001	15632601001	13979301001	15586901001	

36) Hypersensitivity including Infusion-Related Reaction includes MedDRA Terms (MedDRA 25.0) listed in the following table:

MedDRA Term Name	MedDRA Term Name	MedDRA Term Name	MedDRA Term Name
Acquired C1 inhibitor deficiency	Cross sensitivity reaction	Injection site urticaria	Skin necrosis
Acute generalised exanthematous pustulosis	Cutaneous vasculitis	Injection site vasculitis	Skin reaction
Administration related reaction	Dennie-Morgan fold	Instillation site hypersensitivity	Skin test positive
Administration site dermatitis	Dermal filler reaction	Instillation site rash	Solar urticaria
Administration site eczema	Dermatitis	Instillation site urticaria	Solvent sensitivity

MedDRA Term Name	MedDRA Term Name	MedDRA Term Name	MedDRA Term Name
Administration site hypersensitivity	Dermatitis acneiform	Interstitial granulomatous dermatitis	Stevens-Johnson syndrome
Administration site rash	Dermatitis allergic	Intestinal angioedema	Stoma site hypersensitivity
Administration site recall reaction	Dermatitis atopic	Iodine allergy	Stoma site rash
Administration site urticaria	Dermatitis bullous	Kounis syndrome	Stridor
Administration site vasculitis	Dermatitis contact	Laryngeal oedema	Swelling face
Allergic bronchitis	Dermatitis exfoliative	Laryngitis allergic	Swelling of eyelid
Allergic colitis	Dermatitis exfoliative generalised	Laryngospasm	Swollen tongue
Allergic cough	Dermatitis herpetiformis	Laryngotracheal oedema	Symmetrical drug-related intertriginous and flexural exanthema
Allergic cystitis	Dermatitis infected	Limbal swelling	Throat tightness
Allergic eosinophilia	Dermatitis psoriasiform	Lip oedema	Tongue oedema
Allergic gastroenteritis	Device allergy	Lip swelling	Toxic epidermal necrolysis
Allergic hepatitis	Dialysis membrane reaction	Mast cell activation syndrome	Toxic skin eruption
Allergic keratitis	Distributive shock	Mast cell degranulation present	Tracheal oedema
Allergic lymphangitis	Documented hypersensitivity to administered product	Medical device site dermatitis	Type I hypersensitivity
Allergic oedema	Drug eruption	Medical device site eczema	Type II hypersensitivity
Allergic otitis externa	Drug hypersensitivity	Medical device site hypersensitivity	Type III immune complex mediated reaction

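### The hypersensitivity/infusion-reaction summary has no infusion-linked onset window, and its term list has no direct term for 7 of the 13 signs named in Protocol 7.7

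*SAP*

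**What the plan says.** Protocol 7.7 treats infusion reactions as a known risk of the drug: "Infusion-related reactions have been observed during and following administration of RDV". It then gives their presentation: "Signs and symptoms may include hypotension, hypertension, tachycardia, bradycardia, hypoxia, fever, dyspnea, wheezing, angioedema, rash, nausea, diaphoresis, and shivering". It also sets a period of observation after each infusion: "Participants should be monitored for at least 2 hours after the RDV infusion is completed". Protocol 5.3 gives the infusion length ("Remdesivir will be administered via IV infusion over 30 to 120 minutes") and Protocol 3.4 the length of treatment ("Participants will be treated with RDV or saline as placebo for up to 5 days").

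On the analysis side, SAP 7.1.6 plans a combined output: "Hypersensitivity including infusion-related reactions adverse events will also be summarized and listed". Its definition is in SAP Appendix 2, item 36: "Hypersensitivity including Infusion-Related Reaction includes MedDRA Terms (MedDRA 25.0) listed in the following table". The table that follows holds four kinds of term:

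- allergy-specific terms;
- delayed skin reactions, such as Stevens-Johnson syndrome;
- diagnosis-level terms, such as Infusion related reaction and Administration related reaction;
- non-specific haemodynamic terms, including Hypotension, Hypertension, Bradycardia, Blood pressure increased, Circulatory collapse and Shock.

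Item 36 states no timing condition. The general limits are in SAP 7.1.5.1 ("Any AEs with an onset date on or after the study drug start date and no later than 30 days after permanent discontinuation") and in Protocol 8.6, which restricts by-arm safety summaries to the same period. SAP 7.6 declares no departure from the protocol's safety analyses.

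**The concern.** An infusion reaction is defined partly by when it happens, and Protocol 7.7 describes it that way. A definition built only on terms has two weaknesses here.

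The first is specificity. The participants are inpatients with COVID-19 and severely reduced kidney function, some on chronic dialysis. Blood pressure changes and shock can occur in them for reasons unrelated to an infusion. A shock on Day 25 would be tabulated under a heading that names infusion-related reactions.

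The second is sensitivity. Item 36 does not match the protocol's own description. A reaction during the Day 2 infusion that is recorded only as dyspnea, wheezing and chills would not enter the table.

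At stake is how clearly the one dedicated by-arm summary displays a risk that the protocol names.

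**Working it through.** The plan gives no figure to reproduce on this point. The check compares two lists and two time windows.

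**Step 1: signs against terms.** Each sign in Protocol 7.7 is matched to item 36 by name or plain medical equivalent.

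| Sign in Protocol 7.7 | Direct term in item 36 |
|---|---|
| hypotension | Hypotension |
| hypertension | Hypertension |
| bradycardia | Bradycardia |
| angioedema | Angioedema |
| rash | Rash |
| diaphoresis | Hyperhidrosis |
| tachycardia | none |
| hypoxia | none |
| fever | none (nearest: Post procedural fever) |
| dyspnea | none |
| wheezing | none (nearest: Bronchospasm) |
| nausea | none |
| shivering | none (Chills also absent) |

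The result is 6 present and 13 − 6 = 7 absent. Crediting the two near matches leaves 7 − 2 = 5 absent: tachycardia, hypoxia, dyspnea, nausea and shivering.

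**Step 2: is this lost table text?** That is unlikely. The list runs alphabetically down four columns, and each column continues where the one before it stops. Where the absent terms would sit, the neighbours are consecutive. For example, Hypotension is followed by Idiopathic urticaria, Pseudoallergic reaction by Radioallergosorbent test positive, and Multiple allergies by Nephritis allergic.

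**Step 3: the two windows.** For a participant who receives all five doses:

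- General safety window: 5 dosing days + 30 days = 35 days.
- Dosing days only: 5/35 = 14.3%.
- Dosing days plus the day after the last dose (Days 1-6): 6/35 = 17.1%.
- Days outside Days 1-6: 29/35 = 82.9%.
- Infusion time plus the 2 hours of observation: 5 × (0.5 + 2) = 12.5 h to 5 × (2 + 2) = 20 h, out of 35 × 24 = 840 h. That is 1.5% to 2.4%.

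If background events were spread evenly over the window, which is an assumption, about 83% to 86% of them would fall outside a date-based infusion window. A larger share may fall early in an acute illness, so this is not an estimate of how many tabulated events are unrelated.

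**Step 4: what the data can support.** The SAP derives treatment emergence from adverse event onset dates (7.1.5.1), and the study day and last dose from dosing dates (3.8.1). Neither document says whether onset times are recorded. A rule by calendar date is therefore the one they support.

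**The case against.** Much can be said for the plan as written.

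- A reader might infer that the table has no onset window at all. It has one: the period from first dose to last dose plus 30 days applies through Protocol 8.6. What is missing is a window linked to the infusion.
- A reader might infer that real infusion reactions are lost. A reaction recorded as a diagnosis is captured, because item 36 contains Infusion related reaction, Infusion related hypersensitivity reaction, Administration related reaction and Immediate post-injection reaction. Only a reaction coded solely to omitted symptoms is missed, and only in this table. SAP 7.1.6 also tabulates all treatment-emergent events by preferred term and the study drug-related events, so it would appear there.
- A reader might conclude that the table can neither show nor rule out an infusion signal, and try to attach a risk ratio or power figure. The documents do not support that. They give no background rate for these terms, and SAP 7.1.6 plans counts and percentages without a test. Any gain from a window would also depend on how often the added, COVID-like symptoms occur early in the stay.
- The category covers hypersensitivity, including delayed skin reactions. A long window and a broad list are defensible for that part, and a short window on the whole table would be wrong. Moving haemodynamic terms out of the hypersensitivity summary could lose an anaphylaxis coded by its symptoms.
- Protocol 7.7 is text for clinical vigilance and not an analysis definition.

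All of this limits the point without removing it. The general tables do not group the symptoms or tie them to an infusion. Neither document explains why bradycardia is listed and tachycardia is not, or why hypertension is listed and hypoxia is not.

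**Conclusion.** The point holds in a limited form. Item 36 has no infusion-linked window for its infusion-reaction component, and it has no direct term for 7 of the 13 signs in Protocol 7.7 (5 on the lenient count). Followed as written, the table counts non-specific haemodynamic events weeks after the last infusion and leaves out a reaction coded only to the missing symptoms.

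The 7-of-13 count rests on matching by name or plain equivalent. The 83% share of days outside Days 1-6 rests on five doses being given, and it describes calendar time rather than events. Both arms receive blinded infusions and the same rule. The effect is therefore reduced specificity and sensitivity in one descriptive safety summary, with no bearing on the efficacy conclusions.

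**What to change.** Keep the item 36 summary unchanged over the full treatment-emergent window. Beside it, add one row for potential infusion-related reactions, with number and percentage by arm:

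- **Terms:** all item 36 terms plus terms for the seven missing signs (Tachycardia, Hypoxia, Pyrexia, Dyspnoea, Wheezing, Nausea, Chills).
- **Timing:** onset on a date when that participant was dosed, or on the next day.
- **Breakdown within the row:** show separately the diagnosis-level terms, such as Infusion related reaction, and the symptom terms that overlap with COVID-19.

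The added terms and the window belong together, because adding hypoxia, dyspnoea and pyrexia over the full window would mainly add noise.

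The cost is a paragraph in the SAP and one table row. Onset and dosing dates are already collected, and nothing planned is removed. The downside is that a date-based window still admits some coincident same-day events, especially hypoxia, dyspnoea and pyrexia. The breakdown lets the reader see how much of the row they make up.
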